After signing the informed consent all participants will undergo a full blinded baseline medical, functional, nutritional and psychological assessment. Allocation to study group will be revealed to the part of the research team that will carry out the intervention once baseline assessment is completed. The functional capacity assessment will be conducted by a physiotherapist on different days to avoid fatigue related to it, and will consist in a standard incremental cardiopulmonary exercise testing on cycloergometer (CPET), where physiological variables in response to exercise and workload in watts (W) will be measured at the anaerobic threshold and at VO₂ peak, Endurance time (ET) in seconds will be measured by a cycling constant work-rate exercise test performed at a load equivalent of 80% of the peak workload (PWR) the patient could tolerate on the incremental CPET (Ergo- line 900, Ergoline, Bitz, Germany and Ergocard Professional, Medisoft, Sorinnes, Belgium). It will detect the responsiveness of interventions in terms of improved exercise capacity.

Participants will also undergo hand grip strength test (Jamar Hydraulic Hand Dynamometer; Sammons Preston, Bolingbrook, Illinois, USA), 6min walk test (6MWT) and sit-to-stand (STS) test. The 6MWT will assess functional capacity in relation to activities of daily living. Constant work rate exercise test and 6MWT are complementary in the comprehensive evaluation of these patients. Nutritional status will be assessed by a registered dietitian using the Patient Generated Subjective Global Assessment, weight, body mass index, prealbumin and glycosylated hemoglobin (HbA1c). American Society of Anesthesiologists status, Charlson Comorbidity Index and Euroscore II data will be recorded. Physical activity will be measured by the Yale Physical Activity Survey (YPAS), functional capacity by Dukes Activity Status Index questionnaire and Anxiety and depression measured using the Hospital and Anxiety Scale (HADS). All patients will be reassessed using the same tests before undergoing cardiac surgery (T7) and at 3 months postoperatively (T9).

-Procedures

Standard of care (T1–T6): Participants in the control group will follow the standard preoperative protocol at Hospital Clinic de Barcelona that includes physical activity recommendation, nutritional and smoking cessation advice. Moreover, patients suffering from iron-deficiency anaemia will receive intra-venous iron infusion.

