2. Promotion of physical activity and healthy lifestyle: a physiotherapist adequately trained in behavioural strategies will use motivational interviewing techniques to promote physical activity and healthy lifestyle. The motivational interview will focus on empathy, reflective listening and affirmation, and will address the patients' barriers and limitations related to physical activity, to get a change in behaviour.
3. Respiratory physiotherapy: patients will be instructed on daily breathing exercises (chest expansions, diaphragmatic respirations and deep inspirations) with a volumetric incentive spirometer (Coach 2; Smith Medical; London, UK), at least twice per day, 1–2 sets of 10–15 breathings for each exercise.

4. Nutrition counselling and supplementation: participants will meet with a registered dietitian that will assess their nutritional status and their diet based on a self-reported 3-day food diary. Nutritional teaching and a Mediterranean, well-balanced cardioprotective diet will be instructed. An adequate protein intake of 1.2–1.5 g/kg/day will be aimed to meet the European Society for Clinical Nutrition and Metabolism recommendations. If patient does not reach the recommended daily protein intake with diet, protein supplementation with whey protein (Fresubin Protein powder, Fresenius Kabi España) will be provided to reach the aforementioned daily protein intake.
5. Weekly mindfulness sessions: Patients will be invited to attend 1 weekly hourly session of Mindfulness-Based Stress Reduction conducted by a registered psychologist. It will be strongly recommended to those who reported high rates of anxiety and depression on the baseline HADS.

Compliance to the prehabilitation programme will be calculated counting the number of supervised sessions attended out of the total intended sessions. The occurrence of any exercise-related adverse events during the prehabilitation period will be recorded and will be reported immediately to the principal investigator.

Preoperative (T7) and 3-month postoperative functional assessment (T9): All participants' functional capacity will be reassessed before surgery and 3 months postoperative using ET, hand grip strength test, 6MWT and STS test. Anxiety and depression and physical activity questionnaires will be also recorded at these time points.

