Data monitoring: Previous experiences in prehabilitation studies show a clear absence of safety problems related to the experimental procedure. In addition, it is an unmasked trial, which is easier and faster to detect a problem and take appropriate measures.

The investigators of the present study are responsible for ensuring that the study meets the proposed milestones and deadlines. They will also be responsible for all aspects of the study design, management, ethical conduct, analysis and dissemination of results.

Safety data, including new hospitalisation, worsening angina or heart failure and arrhythmias, will be captured and all adverse events will be reported. They are responsible to periodically evaluate the study data for participant safety and study conduct, in addition to making modifications and/or termination of the trial after communication to the Ethics Committee of Clinical investigation of Hospital Clinic de Barcelona.

- *Outcomes*

Clinical outcomes

The primary outcome variable of the study is the incidence of postoperative complications classified following the standards of the European Society of Anaesthesiology and European Society of intensive Care Medicine.

Secondary outcome variables will be: (1) severity of postoperative complications using Dindo-Clavien classification; (2) hospital and ICU days of stay and (3) 3-month and 1-year mortality. Other outcome variables include: (1) ET measured by a cycling constant work-rate exercise testing at 80% of peak oxygen uptake; (2) distance covered in the 6MWT; (3) STS test and hand-grip strength; (4) physical activity by the YPAS and (5) hospitalisation direct costs and use of healthcare resources into the follow-up 1-year period after surgery.

Outcomes for feasibility of prehabilitation include incidence of adverse events during training, compliance to the supervised training sessions and adherence to the programme.

- *Statistical analyses*

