Sample size for this trial has been calculated based on the primary outcome of the study that is the reduction of incidence of postoperative complications in the prehabilitation group. Our own data in a similar population of patients indicated that the incidence of postoperative complications was 30%. Accepting a two-sided alpha-risk of 0.05 and beta-risk of 0.20, anticipating 10% of drop-outs, indicated the need of including 80 participants per group to detect a reduction of the percentage of patients with complications in the intervention group compared with the control group 20%. No adjustment for multiplicity was proposed due to this is a clinical trial with one primary outcome and without needed of interim analyses.

This trial will use intention-to-treat criteria for main analysis; nevertheless, analysis per protocol will also be performed as supportive analysis. Categorical variables, as well primary outcome, will be analysed with Fisher's exact test. Continuous variables will be compared with Student's t-test for independent groups and Mann-Whitney U test according to each variable distribution. Ordinal variables will be analysed by Mann-Whitney U test.

Secondary outcomes looking at the difference between groups for the change in functional capacity over the different time points (repeated measures) will be analysed using generalized estimating equations models and will be shown as estimated effect and their 95%CI. For these analyses, we will apply unstructured matrix in order to assess intra-subject correlation, for cases with no adjustments we will apply an autoregressive model (AR) (1) type matrix.

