Statistical analysis: Randomized groups will be compared for balance on all potentially confounding baseline variables using descriptive statistics and the standardized difference (ASD), which is the difference in means or proportions divided by the pooled standard deviation. Criterion for imbalance will be an absolute standardized difference > 0.10 . Any imbalanced baseline variables will be adjusted for in all analyses below. Data transformations will be made, or non-parametric analyses used to meet model assumptions, as appropriate. Analyses will be intent to treat, with a significance level of 0.05. We will assess the efficacy of the prehabilitation program to standard care on the incidence of POCD using either Pearson chi-square test or logistic regression if there is a need to adjust for baseline imbalance in potentially confounding variables. In either case, the relative risk of developing POCD at 3-months after surgery and its 95% confidence interval will be estimated.

Patient and public involvement

Patient and public involvement was taken into consideration for the development of this protocol. A satisfaction questionnaire was given to a sample of patients who had undergone a prehabilitation programme as part of their clinical pathway before an abdominal surgery. They gave feedback about both the assessments and interventions included in this trial. As a result of their feedback we proceeded to reduce the number of questionnaires given during the assessments, as well as an assessment and intervention redesign, resulting in a more flexible schedule for the participants.

- ETHICS AND DISSEMINATION

Ethics approval for this trial has been obtained by the Ethics Committee of Clinical investigation of Hospital Clinic de Barcelona (HCB/2017/0708). This trial will be conducted according to the principles emanating from the Helsinki Declaration, with compliance to the Good Clinical Practice and the International Council for Harmonisation of Technical Requirements for Pharmaceuticals for Human Use (ICH) guidelines. Confidentiality for participants and their data will be guaranteed according to the Spanish data protection law 'Ley Orgánica de Protección de Datos de Carácter Personal' (15/1999, 13 diciembre) and the General Data Protection Regulation from the European Union (EU 2016/679).

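### Subproject #2 does not say how the T0 value enters the functional-capacity GEE; read in the ordinary way, the analysis is an unadjusted change-score comparison and gives up precision that T0 adjustment would recover

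*Combined protocol and SAP*

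**What the plan says.** Subproject #2 measures endurance time (ET), the 6-minute walk (6MWT), sit-to-stand (STS) and hand grip three times. The baseline section states: "After signing the informed consent all participants will undergo a full blinded baseline medical, functional, nutritional and psychological assessment". It then adds: "All patients will be reassessed using the same tests before undergoing cardiac surgery (T7) and at 3 months postoperatively (T9"). The section on the preoperative and 3-month assessments confirms that functional capacity is "reassessed before surgery and 3 months postoperative using ET, hand grip strength test, 6MWT and STS test".

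The Statistical analyses section takes as its target "Secondary outcomes looking at the difference between groups for the change in functional capacity over the different time points (repeated measures"). These outcomes "will be analysed using generalized estimating equations models and will be shown as estimated effect and their 95%CI". On the correlation structure it says "we will apply unstructured matrix in order to assess intra-subject correlation, for cases with no adjustments we will apply an autoregressive model (AR) (1) type".

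Nothing more is given for this analysis. The section lists no covariates. It does not say whether the response is the change or the raw values at T0, T7 and T9, or whether the two groups share a mean at T0. It does not say whether the reported effect belongs to T7, T9 or both.

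The only rule on baseline adjustment is in the statistical paragraph of the neurocognitive subproject: "Any imbalanced baseline variables will be adjusted for in all analyses below". It is triggered by an absolute standardized difference above 0.10 and governs that subproject's analyses, not these.

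On rank, the Outcomes section places these measures below the secondary outcomes ("Other outcome variables include: (1) ET measured by a cycling constant work-rate exercise testing at 80% of peak oxygen uptake" heads that list), while the Statistical analyses section calls them secondary.

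**The concern.** A between-group difference in change over repeated measures is ordinarily fitted as a group-by-time contrast, with T0 among the responses and a free T0 mean in each group. That contrast is a difference in change scores. It carries the full measurement noise of T0, where a comparison adjusted for T0 uses only the part of T0 that predicts follow-up. The unstructured working correlation does not recover the loss.

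These outcomes show whether the programme improved fitness, which a reader needs in order to interpret any result on complications. The sample size was set for complications alone, so precision on fitness was never planned. Two analysts who follow the section faithfully could also report different estimates and intervals, depending on how each handles T0.

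**Working it through.** **The plan's own figure.** The plan states no precision or power for functional capacity. Its only sample-size figure is 80 per group for complications. That reproduces for 30% against 10%, two-sided alpha 0.05, power 80%, with continuity correction: 72 per group, and 72/0.90 = 80. It is used here only for the number evaluable, 80 × 0.90 = 72 per arm.

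**Inputs.** From the documents: three visits (T0, T7, T9), 1:1 allocation, 72 evaluable per arm. Assumed: a common variance s² at T0 and follow-up, and a T0-to-follow-up correlation ρ between 0.3 and 0.9. The documents give no SD and no ρ for any functional measure.

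**Formulas, n per arm.**

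- Difference in change: variance = (2/n)·s²·2(1−ρ).
- T0-adjusted difference: variance = (2/n)·s²·(1−ρ²), apart from the very small cost of estimating one slope.
- Ratio, adjusted to change: (1−ρ)(1+ρ) / [2(1−ρ)] = (1+ρ)/2. The fraction removed is therefore (1−ρ)/2.
- Difference detectable at 80% power, in SD units: (1.960 + 0.842)·√(2/72) = 0.467, multiplied by √[2(1−ρ)] or √(1−ρ²).

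| Assumed ρ | 2(1−ρ) | 1−ρ² | Variance removed | Per arm needed on change to match 72 adjusted | Detectable difference, change → adjusted (SD) |
|---|---|---|---|---|---|
| 0.3 | 1.40 | 0.91 | 35% | 110.8 | 0.552 → 0.445 |
| 0.5 | 1.00 | 0.75 | 25% | 96.0 | 0.467 → 0.404 |
| 0.7 | 0.60 | 0.51 | 15% | 84.7 | 0.362 → 0.333 |
| 0.8 | 0.40 | 0.36 | 10% | 80.0 | 0.295 → 0.280 |
| 0.9 | 0.20 | 0.19 | 5% | 75.8 | 0.209 → 0.204 |

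**Check by simulation.** 4,000 trials per value of ρ, 72 per arm, three visits with equal correlation between visits.

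- Unstructured fit with free T0 means: the T7 contrast equalled the change-score difference to machine precision.
- T0-adjusted analysis: its variance relative to change was 0.758, 0.827, 0.920 and 0.955 at ρ = 0.5, 0.65, 0.8 and 0.9, against (1+ρ)/2 = 0.750, 0.825, 0.900 and 0.950.
- Unstructured fit with T0 as a response and equal group means at T0: the same ratios as the T0-adjusted analysis.

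**Sensitivity to a chance T0 difference δ.** Given δ, the follow-up means are expected to differ by the treatment effect plus ρδ. Subtracting δ leaves the change contrast off by −(1−ρ)δ. At ρ = 0.6 and δ = 0.2 SD the size is 0.4 × 0.2 = 0.08 SD. With 80 per arm the standard error of a T0 difference is √(2/80) = 0.158 SD, so a gap of 0.2 SD or more arises by chance in about one trial in five. The median shift is about 0.4 × 0.674 × 0.158 = 0.04 SD.

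**The case against.** The strongest reply is that the section fixes no mean model. A repeated-measures GEE with the unstructured correlation it names, T0 as a response and equal group means at T0, already reaches the adjusted variance, leaving about 0% to gain. The remark about cases with no adjustments is also unclear: it may mean a model that fails to fit, or a model without covariates. This stands in part. A reader might infer that the plan has settled on change from T0 and rules out adjustment; the text does not go that far. But it does not state the equal-means constraint either, and its stated target, a difference in change, points towards the less efficient form.

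A reader might also infer bias. Averaged over randomisation the change contrast is unbiased. The shift of −(1−ρ)δ is conditional on the observed T0 gap and is the same inefficiency seen another way; it should not be counted twice.

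Nor would adjustment guarantee removal of every T0 difference. Staff randomise before proposing participation, and the arms sign different consent forms for differently described studies (sections on recruitment and on informed consent). Acceptance could differ by arm, so a T0 gap need not be pure chance. Neither analysis is then automatically unbiased, and a model with equal T0 means shares that limit. This stands, and it is a further reason to fix the handling of T0 in advance.

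Finally, it is tempting to translate the gain into power, with 80% rising to some higher figure. The 80% in the plan belongs to complications, and no functional contrast is powered. The detectable differences above describe precision only.

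**Conclusion.** The point holds as a gap in specification with a clear, free improvement. The plan targets a difference in change in functional capacity and specifies no use of T0 as a covariate. On the ordinary group-by-time reading with free T0 means, adjusting for T0 would cut the variance by (1−ρ)/2: 25%, 15% and 10% at ρ of 0.5, 0.7 and 0.8, with 35% at 0.3 and 5% at 0.9. These figures rest on an assumed ρ, on equal variances, and on that reading of the model; if T0 means are set equal, the loss is about nil. The benefit is precision and less sensitivity to chance imbalance at T0, for outcomes ranked as other or secondary. It does not touch the primary comparison by Fisher's exact test or the 80 per group.

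**What to change.** In the Subproject #2 Statistical analyses section, state the GEE mean model for each functional measure. The responses are the T7 and T9 values. The terms are group, visit, group-by-visit, the participant's own T0 value of that measure, and T0-by-visit. Report the adjusted mean difference and 95% CI separately at T7 and at T9.

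An equally efficient alternative under the unstructured working correlation keeps T0, T7 and T9 as responses and sets group means at T0 equal. It also retains participants who have T0 only, which fits the plan's statement that all randomised patients are analysed. Here the adjustment works through the working correlation, so the condition that triggers the AR(1) fallback should be spelled out as well.

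Apply the chosen rule to YPAS, which is in the same outcome list and is recorded at the same visits. The cost is wording only: T0 assessment is already planned for every participant, and no visit, test or participant is added.

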Surgery and hospital admission (T8): Surgery will take place in the habitual waiting timeframe and will be performed by the regular cardiac surgery teams present in Hospital Clinic de Barcelona. Perioperative clinical protocols will be followed in a usual fashion independently of the group allocation or study participation. Hospital staff, anesthesiologists, surgeons, nurses and other people involved in patient care will be blinded to the study arm. Intraoperative complications or events as well as the need blood product transfusion or any deviation from normal course will be recorded in the intraoperative case report form (CRF).

The primary outcome of this study is the incidence of postoperative complications before patient discharge from the hospital. The type of complications included will be classified following the standards of the European Society of Anesthesiology and the European Society of Intensive Care medicine: Acute kidney injury, acute respiratory distress syndrome, arrhythmia, cardiac arrest, cardiogenic pulmonary oedema, deep vein thrombosis, delirium, gastrointestinal bleed, infection, source uncertain, laboratory confirmed bloodstream infection, myocardial infarction, pneumonia, paralytic ileus, post-operative haemorrhage, pulmonary embolism, stroke, surgical site infection and urinary tract infection.

The severity of complications will be also recorded, as a secondary outcome measure, following the Clavien- Dindo classification. To ensure accuracy of the primary endpoint, the data will be collected by a physician member of the team, every day according to standard clinical care, and then reviewed by another researcher. Both of them will be

blinded to the study group to avoid bias. Patient- chargeable costs (ie, pharmacy and blood bank); tariff- chargeable costs (ie, medical care, diagnostic techniques, laboratories, interconsultations); other healthcare resources use (ie, ICU stay, total hospitalisation length of stay, readmissions, emergency room visits) and survival will be also assessed at 3 months and 1 year postcardiac surgery by chart review.

Data collection management and monitoring: All participant's de-identified data collected at different time points will be entered by research staff members into Research Electronic Data Capture (REDCap) CRF via a secure webpage interface. Online data will be stored in a safe server located the Hospital

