A cost-effectiveness study will be carried out from the perspective of the hospital, taking into account the costs of the intervention and the expenses related to the disease during the follow-up (30 days). For costs, the mean or median and their 95%CI of difference in per-patient costs between the two groups will be computed (control-group costs minus prehabilitation-group costs), so that positive values will be interpreted as savings of the prehabilitation programme. Considering previous experience with prehabilitation cost analysis, a highly skewed distribution will probably be present. Right-sided asymmetric distribution appears when some patients incur in high costs, mainly because of major medical complications. To deal with this, a non-parametric approach (bootstrapping) will be used. Bootstrap analysis yields more robust when dealing with skewed cost data compared with non-parametric tests.

- Perioperative neurocognitive disorders subproject

Inclusion criteria: Patients included in the main study with age ≥ 50 years.

Exclusion criteria: Those applied for the main study. Additionally, reading difficulties, and non-Spanish or Catalan native speakers will also be excluded.

Baseline cognitive assessment (T0): We selected a battery of tests with input from a neurologist and a neuropsychologist – both experts on cognitive disorders. Two blinded-trained professionals ([name]) will perform the cognitive assessment in a quiet

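### Subproject #2's cost-effectiveness and savings analysis uses a 30-day follow-up with no stated start, although the cost and resource-use outcome is defined and collected to 1 year after surgery

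*Combined protocol and SAP*

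**What the plan says.** Three places in Subproject #2 bear on this, all in current text.

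- **Statistical analyses, cost-effectiveness paragraph.** The plan announces a cost-effectiveness study from the hospital's perspective and sets its scope as "taking into account the costs of the intervention and the expenses related to the disease during the follow-up (30 days"). The start of the 30 days is not given. The next sentence defines the per-patient difference as control minus prehabilitation and fixes its reading: "positive values will be interpreted as savings of the prehabilitation programme". That sentence names no horizon of its own, so the 30 days carry over from the sentence before. Bootstrapping is prescribed because a skewed distribution is expected, in which "some patients incur in high costs, mainly because of major medical complications".
- **Outcomes, Clinical outcomes.** The fifth of the other outcome variables, listed after the primary and the three secondary outcomes, is "hospitalisation direct costs and use of healthcare resources into the follow-up 1-year period after surgery".
- **Surgery and hospital admission (T8).** One sentence takes together patient-chargeable costs, tariff-chargeable costs and "other healthcare resources use (ie, ICU stay, total hospitalisation length of stay, readmissions, emergency room visits"), and ends by saying that these and "survival will be also assessed at 3 months and 1 year postcardiac surgery by chart review".

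**The concern.** The outcome is set over one period and the only cost-specific analysis over another. Two analysts who start from different sections would produce different savings figures, each able to cite the plan. With the horizon open in this way, it could also be settled after the results are seen.

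The difference is not cosmetic. The 30-day analysis counts the intervention's cost but only a short stretch of later hospital use. The plan itself attributes high costs mainly to major complications. It is reasonable, though not shown in the documents, to expect some of those patients to return after day 30. Their later readmissions and emergency visits would be collected and then left out of the figure that the plan calls savings.

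**Working it through.** **1. The horizons side by side.**

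- Cost-effectiveness and savings analysis: 30 days, start not stated (Statistical analyses).
- Cost and resource-use outcome: 1 year after surgery (Outcomes).
- Data collection for costs and resource use: 3 months and 1 year after surgery (Surgery and hospital admission).

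No section explains the shorter horizon, calls it a short-term analysis, or plans a 1-year cost-effectiveness or sensitivity analysis.

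**2. Share of the window.** If the 30 days start at surgery, the analysis covers 30/365 = 8.2% of the outcome window. The other 365 − 30 = 335 days, or 335/365 = 91.8%, lie outside it. If the 30 days start at discharge after an index stay of L days, the covered share is (L + 30)/365, and L is not given. Both are shares of time. They say nothing about the share of cost.

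**3. What is left out of the savings estimate.** Count days from surgery and let D(t) be the control-minus-prehabilitation mean cost up to day t, with the programme's cost included. Then

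D(365) = D(30) + [control cost, days 31–365 − prehabilitation cost, days 31–365].

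The programme's cost is in both D(30) and D(365), so it cancels from the gap between them. The gap is the bracket alone. It is positive if prehabilitation patients use less hospital care after day 30, negative if they use more, and zero if the arms are alike. The documents give no cost, readmission rate or late-complication rate, so the bracket cannot be evaluated in size or sign.

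**4. Does a narrower reading remove the conflict?** The 1-year phrase in the Outcomes section could be read as qualifying only resource use and not hospitalisation costs. The data-collection sentence counts against this, because it puts cost items and resource use together at 3 months and 1 year. Even on the narrow reading, readmissions and emergency visits after day 30 belong to the outcome but not to the savings estimate.

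**The case against.** The best defence is that the two horizons can coexist. A 30-day cost-effectiveness study and a 1-year cost outcome are different results, and the general tests for continuous variables (Student's t or Mann-Whitney) could compare 1-year costs. This stands in part: a reader might infer that 1-year costs go unanalysed, and the documents do not support that. But those tests would give no savings estimate from the prescribed bootstrap, and the plan itself regards bootstrapping as more robust than non-parametric tests for skewed costs. Nor does the plan present the two results as separate.

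Two further objections limit the point.

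- **Long index stays.** A reader might infer that a long surgical admission is cut off at day 30. That follows only if the clock starts at surgery. If it starts at discharge, the whole admission is counted. The plan does not say which, and that is a gap in its own right.
- **Timing of complication costs.** The primary outcome counts complications before discharge, so much of their cost may fall inside either horizon. The omission is real, but it may be small.

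**Conclusion.** The inconsistency holds. The savings analysis and the outcome it should serve have different horizons, the shorter one has no start point, and later resource use that is due to be collected does not enter the savings estimate. This rests on the wording of the three sections and on no assumed figure. The effect on estimated savings is unknown in size and direction.

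Two stronger conclusions are tempting and should not be drawn.

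- **That the cut-off decides whether the programme appears to save money.** Any euro figure would have to be assumed. For example, a 5-percentage-point difference in major complications at EUR 5,000 to 20,000 each after day 30 gives 0.05 × 5,000 = EUR 250 to 0.05 × 20,000 = EUR 1,000 per patient. None of these inputs is in the documents, and neither is a programme cost to set the result against. Later costs could also run the other way.
- **That saving money is a stated objective of the trial.** Costs are listed only among the other outcome variables, which limits the weight of the point.

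The matter is worth correcting because the correction is cheap and removes a choice that could otherwise be made after the data are seen. It does not touch the primary analysis or the sample size.

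**What to change.** In the cost-effectiveness paragraph of Subproject #2:

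- Make the main cost analysis the bootstrapped control-minus-prehabilitation difference in programme cost plus hospital costs from the surgical admission through 1 year after surgery. Base any statement about savings on it.
- Keep the 30-day result as a labelled secondary analysis, and state whether the 30 days run from surgery or from discharge.
- State how deaths and incomplete 1-year follow-up are handled. Include any randomised patient who does not reach surgery, since the main analysis is by intention to treat and the window is anchored on surgery.

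The cost window should not start at randomisation. Under the plan's recruitment procedure, randomisation comes before the research staff meet the patient and so before consent. No section plans to collect both arms' general healthcare costs between randomisation and surgery, so that start would need new data capture.

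The cost is a change of SAP wording, some extra analysis work and probably a wider confidence interval than at 30 days. The 1-year data are already planned by chart review.
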